3.3.2 Secondary endpoints

- i. The proportion of eligible recipients who consent to take part in the study.
- ii. The proportion of eligible donor cardiac allografts where randomisation occurs according to the Protocol.
- iii. The proportion of eligible donor cardiac allografts where the heart is preserved in the correct randomly allocated solution.
- iv. Key outcome completeness
- v. The development of Primary Graft Dysfunction, according to the 2014 ISHLT Consensus Definition(2), within 24 hours of transplant implantation.
- vi. Echocardiographic parameters from trans-oesophageal echo immediately after transplant implantation, including:
 - a. Left Ventricular ejection fraction
 - b. Left ventricular maximal posterior wall thickness
 - c. Maximal septal wall thickness
 - d. Left ventricular function
 - e. Right ventricular function
 - f. The presence/absence of regional wall motion abnormalities
- vii. 30-day all-cause mortality.
- viii. 6-month survival rates, determined at the end of the study.
- ix. Development of the following post-operative complications will be recorded:
 - a. Dysrhythmias (defined by the clinical team) within 30-days of transplant implantation
 - b. Myocardial Infarction (defined according to ESC definitions of myocardial infarction post cardiac surgery) within 30-days of transplant implantation
 - c. Stroke (defined by radiological evidence of ischaemia/haemorrhage and clinical symptoms of stroke) within 30-days of transplant implantation
 - d. Transplant rejection (defined by the clinical team and confirmed on histopathology of biopsy material or post-mortem) within 30-days of transplant implantation
 - e. The need for post-operative renal replacement therapy within 30-days of transplant implantation
 - f. Infection (from any source requiring antibiotic therapy) within 30-days of transplant implantation
 - g. Venous thromboembolism (defined by radiological evidence and need for treatment) within 30-days of transplant implantation
 - h. Re-admission to any UK hospital within 30 days of transplant implantation
 - i. Hyponatraemia within 24 hours of transplant implantation (Na<125mEq/L on any serum laboratory-analysed sample, not blood gas analysis)
- x. Median length of initial ICU stay in hours
- xi. Median length of initial hospital stay in days

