- iii. Body surface area calculated using the DuBois and DuBois formula: Body Surface Area= 0.007184 x (Height(m) $^{0.725}$) x (Weight(kg) $^{0.425}$).
- iv. Mean Arterial Pressure (mmHg) on invasive intra-arterial blood-pressure monitoring at the time of Swan-Ganz measurements.
- v. Central Venous Pressure (mmHg) on invasive central venous pressure monitoring at the time of Swan-Ganz measurements.

As this is an exploratory outcome measure, with the intent to assess its utility based on real-world data, this will be assessed based on the above data being recorded on the intensive care electronic health record system. The measurements will be taken and recorded by the healthcare professional(s) looking after the participant. Where the outcome assessor transferring this data from the healthcare record to the trial database cannot find a measurement within the stipulated timeframe, this will be treated as missing data.

PGD will be determined based on the ISHLT consensus statement 2014 (2) and graded accordingly. PGD is defined as occurring within 24 hours, therefore all measurements included below must be taken within the first 24 hours after admission to ICU post-transplant procedure. Its definition requires the following variables to be recorded on the database:

F-CUSToS Protocol

Version Number 2.0; Dated 30 January 2025

- Ejection fraction on echocardiogram; where multiple measurements are taken the lowest estimate of ejection fraction recorded will be inputted to the database.
- ii. Haemodynamic variables taken at the time of a Swan Ganz measurement*:
 - (i) Central Venous Pressure (mmHg)
 - (ii) Pulmonary capillary wedge pressure (mmHg)
 - (iii)Cardiac Output (L/min)
 - (iv) Cardiac Index (L/min/m2)
 - (v) Mean Arterial Pressure (mmHg)
 - (vi)Transpulmonary gradient (mmHg)
 - (vii) Pulmonary artery systolic pressure (mmHg)
- iii. Vasoactive Inotrope Score (VIS), where VIS = dopamine [μ g kg⁻¹ min⁻¹] + dobutamine [μ g kg⁻¹min⁻¹] + 100×adrenaline [μ g kg⁻¹ min⁻¹] + 50×levosimendan [μ g kg⁻¹ min⁻¹] + 10×milrinone [μ g kg⁻¹ min⁻¹] + 10 000×vasopressin [units kg⁻¹ min⁻¹] + 100×noradrenaline dose [μ g kg⁻¹ min⁻¹].
- iv. Presence/absence of an intra-aortic balloon pump (IABP).
- v. Presence/absence of mechanical circulatory support (ECMO/LVAD/RVAD/BiVAD).

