*Where multiple Swan Ganz measurements are taken within the first 24 hours after transplant, the set of variables taken at the same time as the highest inotrope score should be uploaded to the CRF. Where there are multiple Swan Ganz measurements with the same inotrope score the set of variables with the lowest cardiac output should be uploaded to the CRF.

The following echocardiographic parameters from trans-oesophageal echo immediately after transplant implantation will be recorded in the initial outcome data collection CRF:

- i. Left Ventricular ejection fraction (% estimated by Simpson's biplane method)
- ii. Left ventricular maximal posterior wall thickness (in mm)
- iii. Maximal septal wall thickness (in mm)
- iv. Left ventricular function (good, moderate, poor or very poor)
- v. Right ventricular function (good, moderate, poor or very poor)
- vi. The presence/absence of any regional wall motion abnormalities as determined by the TOE operator

30-day outcome data collection: The delegated individual(s) in the recipient centre should upload the 30-day mortality, postoperative complication, length of initial ICU stay, and length of initial hospital stay data, on the 31st day after the transplant procedure. This should be conducted in accordance with the blinding instructions laid out in section 7.4 of this Protocol. The variables will be entered into the CRF as follows:

- i. 30-day mortality: alive/dead
- ii. Post-operative complications:
 - (i) Dysrhythmias (any within 30 days):
 - 1. Atrial fibrillation yes/no
 - 2. Ventricular tachycardia yes/no
 - 3. Ventricular fibrillation yes/no
 - 4. Other rhythm abnormality yes/no (specify)
 - (ii) Myocardial Infarction within 30 days (defined according to ESC definitions of myocardial infarction post-cardiac surgery): yes/no

- (iii)Stroke within 30 days (defined by radiological evidence of ischaemia/haemorrhage and clinical symptoms of stroke): yes/no
- (iv)Transplant rejection within 30 days (defined by the clinical team and confirmed on histopathology of biopsy material or post-mortem): yes/no
- (v) Infection within 30 days (from any source requiring antibiotic therapy): yes/no (specify suspected source)
- (vi) Venous thromboembolism within 30 days (defined by radiological evidence and need for treatment): yes/no (specify PE/DVT)
- (vii) 30-day re-admission to any UK hospital: yes/no
- (viii)Hyponatraemia within 24 hours of transplant (Na<125mEq/L on serum sample, not blood gas analysis): yes/no

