9.3 Recording and reporting of SAEs, SARs AND SUSARs

All SAEs/SARs/SUSARs occurring from the time of perfusion of the treatment into the aortic root until 24 hours post-transplant must be recorded on the electronic AE Form **within 24 hours** of the research staff becoming aware of the event. NB 24 hours post has been chosen because all the IMP is washed out on reperfusion of the heart and cannot reasonably be expected to still be present or have any direct effect beyond 24 hours. "Post-transplant" will be defined as the time the recipient leaves the operating theatre after they receive their transplant or death where this

occurs during the transplant implantation. Death during the implantation would be considered a SAE and should be recorded as such, with the PI review of expectedness in relation to the IMP.

For each SAE/SAR/SUSAR the following information will be collected:

- i. full details in medical terms and case description
- ii. event duration (start and end dates, if applicable)
- iii. action taken
- iv. outcome
- v. seriousness criteria
- vi. causality (i.e., relatedness to trial drug / investigation), in the opinion of the investigator
- vii. whether the event would be considered anticipated.

Any change of condition or other follow-up information should be emailed to the Sponsor as soon as it is available or at least within 24 hours of the information becoming available. Events will be followed up until the event has resolved or a final outcome has been reached.

For any other complication, not listed above in section 9.2, occurring within 24 hours of the transplant implantation the information listed above must be collected. However, it will then be the responsibility of the PI to determine whether or not this is likely to be related to the IMP-treatment. If it is deemed likely to be related it will be termed an AR. The PI will also have responsibility for determining the level of seriousness, according to definitions outlined in section 9.1. If an AE/AR is assigned by the PI or delegate (or following central review) as serious it will be termed and SAE/SAR. As there is no reference safety information for either treatment in the trial, all SARs will automatically be treated as SUSARs and will be subject to expedited reporting to the Medicines and Healthcare Products Regulatory Agency (MHRA). The sponsor will inform the MHRA, the REC and Marketing Authorisation Holder of SUSARs within the required expedited reporting timescales.

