- xiii. Smoking, a categorical variable with categories current, previous and never, reported as proportions.
- xiv. Drug abuse, a categorical variable with categories current, previous and never, reported as proportions.
- vv. Vasoactive Inotrope score (VIS), a continuous variable calculated as VIS = dopamine (×1) + dobutamine (×1) + amrinone (×1) + milrinone (×15) + adrenaline (×100) + noradrenaline (×100), with each drug dosed in $\mu g/kg/min$. using the maximum dosing rates of vasoactive and inotropic medications ($\mu g kg^{-1} min^{-1}$) or IU $kg^{-1}min^{-1}$) in the 24 h prior to the transplant implantation, reported as medians.
- xvi. Mechanical Circulatory Support, a categorical variable with categories None, VA-ECMO, VV-ECMO, IABP, LVAD, RVAD, BiVAD, TAH, Impella and Other, determined by their use at the time of transplant (prior to implantation) and reported as proportions.
- xvii. Previous cardiac surgery, a categorical variable with categories yes/no, reported as proportions.
- xviii. Pre-operative mean pulmonary artery pressure (mmHg), pulmonary capillary wedge pressure (mmHg), cardiac output (L/min) and cardiac index (L/min/m2), continuous variables taken from the right heart catheter prior to transplant implantation, reported as medians.

A consort flow diagram will be produced and appended to this Protocol. This will evaluate all eligible transplant procedures as part of the primary outcome of this feasibility study, but will also record all patients approached to consent, some of whom may not be included in the primary outcome, for example recipients who have been approached to consent prior to their transplant but do not receive a transplant within the study period.

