10.8 Procedure(s) to account for missing or spurious data

Any missing or spurious data identified at the time of CRF submission will result in a telephone call to the centre's PI to identify if the data can be completed. If not, missing data will be assumed to be missing at random for the purposes of secondary analyses and therefore not imputed. Robust estimators will be used if, after checks, notable outliers are remaining.

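### The PGD time window is inconsistent, and the version tied to ICU admission excludes theatre data and gives a death in theatre no PGD status

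*Protocol*

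**What the plan says.** **Time origin.** Protocol 3.3.2 (v) sets the endpoint as "The development of Primary Graft Dysfunction, according to the 2014 ISHLT Consensus Definition(2), within 24 hours of transplant implantation". Section 7.7, which governs data entry, says "PGD is defined as occurring within 24 hours, therefore all measurements included below must be taken within the first 24 hours after admission to ICU". The footnote to the same list starts "Where multiple Swan Ganz measurements are taken within the first 24 hours after transplant". The endpoint table in 3.3.4 measures PGD at 24 hours post-transplant.

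**Data admitted.** The 7.7 list takes the lowest ejection fraction on echo, one set of Swan-Ganz variables, an inotrope score, and the presence or absence of a balloon pump or mechanical support. The trans-oesophageal echo (TOE) done straight after implantation goes on the same CRF, but in a separate list. Appendix 2 schedules that TOE at implantation and no other echo; its 24-hour column has a right heart catheter and blood tests.

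**Death in theatre.** Section 9.3 foresees it: "Death during the implantation would be considered a SAE and should be recorded as such". No section gives such a recipient a PGD status. Under 10.8, after a telephone query to the centre, "missing data will be assumed to be missing at random for the purposes of secondary analyses and therefore not imputed".

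**Use of PGD.** It is the intended primary outcome of the 400-patient trial (section 2). It also feeds the DSMC concern at a rate above 50% and the early-cessation criterion of a 30-point difference (7.10).

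**Inotrope score.** For PGD, 7.7 weights milrinone ×10, levosimendan ×50 and vasopressin ×10,000. For donor and recipient baseline, 10.3.1 gives "VIS = dopamine (×1) + dobutamine (×1) + amrinone (×1) + milrinone (×15) + adrenaline (×100) + noradrenaline (×100", with neither levosimendan nor vasopressin.

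**The concern.** A 24-hour endpoint needs one starting point. Here the endpoint definition and the data rule start at different events, and the rule in 7.7 is worded as mandatory. Whatever is measured between completion of implantation and arrival in ICU lies inside the endpoint but outside the admissible data.

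Two consequences follow. The ejection fraction for PGD cannot come from the scheduled theatre echo, so it depends on an ICU echo that the schedule does not require. And a recipient who never reaches ICU cannot be classified. Leaving that recipient out as missing at random is hard to defend when graft failure may be the reason the data do not exist.

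At stake are a rate that the DSMC is asked to act on and the rehearsal of the main trial's primary outcome; section 4 says the design replicates that trial apart from the primary outcome.

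**Working it through.** **1. The windows side by side**

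| Place | Clock starts at | Theatre TOE admitted? | Theatre death classifiable? |
|---|---|---|---|
| 3.3.2 (v) | implantation | yes | yes |
| 7.7, main rule | ICU admission | no | no |
| 7.7, footnote | transplant | unclear | unclear |

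Section 9.3 defines post-transplant as leaving theatre, or death during implantation, but for safety reporting only.

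**2. What the 7.7 rule loses and keeps.** Balloon pump and mechanical support are recorded as present or absent with no start time, so support begun in theatre and still running in ICU is captured. So are inotropes and poor function that persist. Lost are death in theatre, and dysfunction or support seen only in theatre.

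**3. The DSMC limit (scenario).** Assume 25 per arm (50 patients, 1:1) and 13 PGD events in one arm, one of them a death in theatre.

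- All counted: 13/25 = 52.0%, above 50%.
- Theatre death dropped as missing: (13 − 1)/(25 − 1) = 12/24 = 50.0%, not above 50%.

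**4. The reported rate (scenario).** Assume 9 events among 25 (36%, the protocol's UK estimate) with k lost.

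| k | dropped as missing, (9 − k)/(25 − k) | counted as no PGD, (9 − k)/25 |
|---|---|---|
| 1 | 33.3% | 32% |
| 2 | 30.4% | 28% |
| 3 | 27.3% | 24% |

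**5. Main-trial power.** Inputs from section 2: 36% versus 22%, power 0.85, two-sided 0.05, N = 400.

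n per arm = [1.960·√(2·0.29·0.71) + 1.036·√(0.36·0.64 + 0.22·0.78)]² / 0.14², which gives 188 (376 in all). With the continuity correction it is 202 (404 in all), so the stated 400 reproduces. Uncorrected power at 200 per arm is 0.873.

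Let a share s of PGD events be lost equally in both arms (s is assumed). Counted as no PGD, each rate p becomes p(1 − s). Dropped as missing, it becomes p(1 − s)/(1 − ps) with 200(1 − ps) patients per arm.

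| s | rates if counted as no PGD | power | rates if dropped | power |
|---|---|---|---|---|
| 2% | 35.3 / 21.6% | 0.863 | 35.5 / 21.7% | 0.868 |
| 5% | 34.2 / 20.9% | 0.848 | 34.8 / 21.1% | 0.860 |
| 10% | 32.4 / 19.8% | 0.821 | 33.6 / 20.3% | 0.846 |
| 15% | 30.6 / 18.7% | 0.791 | 32.4 / 19.3% | 0.831 |

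**6. Inotrope score.** Same illustrative infusion rates, 7.7 formula against 10.3.1 formula:

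- milrinone 0.5 µg/kg/min: 10 × 0.5 = 5.0 against 15 × 0.5 = 7.5;
- vasopressin 0.0005 units/kg/min: 10,000 × 0.0005 = 5.0 against 0.

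The 10.3.1 text also mentions IU per kg per minute, a unit that none of its listed drugs uses.

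**The case against.** The strongest reply is that this is a wording mismatch with little effect. Severe graft failure will usually still be visible in ICU, where 7.7 records it. Theatre deaths are reported as SAEs, investigated under 9.5, counted in 30-day mortality and covered by a separate DSMC survival limit. A window opening at ICU admission also closes later, so it can add events as well as lose them. The handling of deaths before assessment often belongs in the SAP, which is not shown. PGD is a secondary endpoint here.

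Much of this stands. A reader might infer that all graft failure in theatre is lost, or that theatre deaths vanish from the trial; neither is so. Nor do the documents show that a poorer solution would look better: that needs unequal loss between arms, and no rate of theatre loss is given for either arm. With equal loss of 5% of events dropped as missing, power stays at 0.860, above the stated 0.85.

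It might also be inferred that the two inotrope formulas could grade one patient's PGD differently. They could not. The 10.3.1 formula covers the 24 hours before donation or implantation, and only the 7.7 formula enters PGD.

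What the reply does not remove is the contradiction. The ICU-admission rule is fixed in the protocol, it is mandatory, and it determines what reaches the CRF. A SAP cannot analyse an ejection fraction or support episode that was ruled out at entry. Section 1 describes PGD as graft failure in the first 24 hours after transplant without a discernible cause, which a theatre death can satisfy, yet 7.7 gives it no route into the endpoint.

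**Conclusion.** The point holds in a limited form and should be corrected. The time origin for PGD differs between 3.3.2, the 7.7 rule and the 7.7 footnote. The 7.7 rule shuts out the only scheduled echo and events confined to theatre, and it leaves a theatre death to be omitted under an assumption that may be false for exactly that patient.

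The size cannot be derived from the documents. With 25 per arm, one omitted death can decide whether the DSMC limit is crossed (52% against 50%), but that rests on an assumed 13 events and one theatre death. The power figures rest on an assumed loss of 2% to 15% of events, equal in both arms. The feasibility primary endpoint and its success rule are unaffected.

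The inotrope score is a separate, minor matter of one name for two scales: pre- and post-transplant values are not comparable and could be miscoded.

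**What to change.** 1. Reconcile 3.3.2, the 7.7 rule and its footnote (and the 3.3.4 table) to one window, running from completion of implantation to 24 hours. State that the theatre TOE ejection fraction and support used in theatre after implantation are admissible.
2. State in 7.7 that a death in theatre from graft failure with no other discernible cause counts as a PGD event, and add to 10.8 that it is not treated as missing at random.
3. Reconcile the inotrope formulas in 7.7 and 10.3.1 to one, or give them different names and say that they are not to be compared.

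The cost is wording plus a small CRF edit. The theatre TOE is already on the CRF. Support started and removed in theatre may need a new field, because 7.7 takes operative data from the NHSBT registry and nothing shows that the registry holds this item. Donor and recipient baseline data also come from the registry, so any change to the baseline score should be checked against what it supplies.

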1 BACKGROUND

Primary graft dysfunction (PGD) is the leading cause of early mortality after cardiac transplantation, occurring in approximately one-third of cases, with a mortality rate of around 20%(1). PGD was defined, in an ISHLT consensus statement in 2014, as graft failure occurring in the first 24 hours after transplant, not as a result of a discernible cause(2). As a result of this definition, the causes of PGD are complex and difficult to investigate. Lund et al.(3) highlighted the importance of cold ischaemic time as a predictor of mortality, with increasing cold ischaemic time leading to increased short- and long-term mortality. Outcomes significantly deteriorate with a cold ischaemic time greater than 6 hours(4). The principal issues affecting the cold ischaemic heart are the loss of Adenosine Triphosphate (ATP), cellular swelling, extra-cellular oedema, cellular acidosis, calcium overload, endothelial injury and the build-up of oxygen free radicals, which contribute to mitochondrial damage(5). In turn, the release of these toxic metabolites on reperfusion of the heart can cause further injury, termed reperfusion injury. It is the purpose of the cardioplegia/myocardial preservative solution to mitigate these effects and the consensus statement of 2014 specifically highlights "better preservation", including "different additives in solutions", as a prevention strategy for PGD(2).

There are several solutions available and approved for use as myocardial preservatives in cardiac transplantation around the world. In the UK only two solutions are in current use: Sterile Concentrate for Cardioplegia Infusion (Martindale Pharmaceuticals), commonly referred to as St Thomas' Solution, and sometimes marketed as Plegisol; and Custodiol-HTK solution ([name] Köhler Chemie GMBH), sometimes referred to as Bretschneider solution. Currently, St Thomas' solution is used in around 90% of UK heart transplants, primarily because of familiarity and cost, having been developed in the UK and being slightly cheaper than Custodiol-HTK.

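### The data listed for classifying primary graft dysfunction (PGD) include no discernible-cause item, so the data set cannot show whether known-cause dysfunction was excluded.

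*Protocol*

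**What the plan says.** Protocol section 1 describes PGD, under the 2014 consensus, as "graft failure occurring in the first 24 hours after transplant, not as a result of a discernible cause". The definition therefore has a positive part (graft failure within 24 hours) and a negative part (no cause found).

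Section 3.3.2, item v, makes PGD by that consensus a secondary endpoint. Section 7.7 repeats the rule: "PGD will be determined based on the ISHLT consensus statement 2014 (2) and graded accordingly". It then introduces the data list with "Its definition requires the following variables to be recorded on the database". The list has five groups:

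- ejection fraction (the lowest recorded value);
- haemodynamics at a Swan-Ganz measurement;
- the Vasoactive Inotrope Score;
- balloon pump, present or absent;
- mechanical circulatory support, present or absent.

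These data are due within 72 hours of the transplant. The 30-day form, completed on day 31, has separate items for myocardial infarction and rejection. The rejection item reads "Transplant rejection within 30 days (defined by the clinical team and confirmed on histopathology of biopsy material or post-mortem): yes/no".

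The PGD rate is used in three places: the secondary endpoint (3.3.2, with Hypothesis 1 in 3.2); the DSMC concern limit of more than 50%, set against a UK estimate of 36% (7.10); and the planned 400-patient trial, sized on 36% versus 22% (2 and 10.2).

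**The concern.** The list is presented as what the definition needs, yet every group describes whether the heart is failing and how badly. None records whether a cause was looked for, found or ruled out, and that is the part of the definition that makes dysfunction primary. The protocol describes no adjudication step and no site-level PGD judgement that would carry this information.

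An analysis plan cannot repair this later, because it cannot recover an exclusion that was never recorded. At stake is the interpretation of the PGD rate in its three uses. Section 4 says the study replicates the larger trial except for its primary outcome, so the same gap could pass into a trial in which PGD is the primary endpoint.

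**Working it through.** **Step 1: definition against data.**

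| Element in section 1 | Item in the 7.7 PGD list |
|---|---|
| Graft failure | Ejection fraction, haemodynamics, inotrope score, balloon pump, mechanical support |
| Within 24 hours | Measurements restricted to the first 24 hours after ICU admission |
| No discernible cause | None |

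**Step 2: can another item supply the cause?**

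- Rejection and myocardial infarction (7.7, 30-day data) are yes/no over 30 days, with no date and no link to the graft failure. A yes cannot be placed in the first 24 hours.
- Bleeding and return to theatre are not outcome items in 3.3.2 or 7.7.
- Section 9.2 places return to theatre for bleeding, myocardial infarction and acute or hyperacute rejection among expected complications outside the operational SAE definition. Safety reporting will not reliably capture them.
- Regional wall motion on the post-implant echo, transpulmonary gradient, pulmonary artery pressure and pre-operative pulmonary pressures bear on cause but do not attribute one.
- Operative data come from the registry (7.7), with no cause-of-dysfunction item named.

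No listed item gives a dated, attributable cause.

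**Step 3: the plan's own figure.** Inputs from 10.2 are 36% versus 22%, two-sided 5%, power 0.85 and 400 patients, with 1:1 allocation from section 4 (200 per arm). The formula is

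power = Φ[(d − 1.96·SE0)/SE1], where d = p1 − p2, SE0 = √(2·p̄(1−p̄)/n), SE1 = √((p1(1−p1) + p2(1−p2))/n), and p̄ is the mean of p1 and p2.

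With n = 200: d = 0.14, p̄ = 0.29, SE0 = 0.04538, SE1 = 0.04483. Power = Φ(1.139) = 0.873. For power 0.85 the total is 376 without continuity correction and 404 with it, so the stated 400 is reproduced closely.

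**Step 4: illustration of size.** The documents give no rate of known-cause dysfunction. Assume a share q of hearts without PGD meets the severity criteria for another reason and is counted. Then p′ = p + (1 − p)q in each arm. For q = 0.05: 0.36 + 0.64 × 0.05 = 0.392 and 0.22 + 0.78 × 0.05 = 0.259; d = 0.133, SE0 = 0.04686, SE1 = 0.04638, power = Φ(0.8875) = 0.813.

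| Assumed q | Rates (%) | Difference (points) | Power, 200 per arm | Chance that a 25-patient arm exceeds 50% |
|---|---|---|---|---|
| 0 | 36.0 / 22.0 | 14.0 | 0.873 | 7.4% |
| 2% | 37.3 / 23.6 | 13.7 | 0.849 | 9.6% |
| 5% | 39.2 / 25.9 | 13.3 | 0.813 | 13.5% |
| 10% | 42.4 / 29.8 | 12.6 | 0.748 | 22.0% |
| 15% | 45.6 / 33.7 | 11.9 | 0.683 | 32.8% |

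The arm with less PGD rises more, because it has more hearts left to misclassify (at 5%, +3.9 against +3.2 points). That is why the difference shrinks. The last column is the binomial probability of 13 or more of 25 at the higher of the two rates. It assumes a single look at a complete arm; 7.10 gives neither denominator nor timing.

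**Step 5: the alternative model.** Suppose the 36% already contains a fraction f of known-cause cases that the solution cannot affect, with the same relative reduction (0.22/0.36) in the rest. The lower rate is then 0.22(1 − f) + 0.36f. For f = 5%, 10% and 20% this is 22.7%, 23.4% and 24.8%, and power is 0.834, 0.790 and 0.684.

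**The case against.** The strongest reply is that the exclusion already sits in the governing rule. Sections 3.3.2 and 7.7 both invoke the consensus, and nothing says PGD is computed from the listed fields alone, so an assessor following the rule would apply the exclusion. This stands in part. A reader might infer that the study will measure all early graft dysfunction; the documents do not establish that. What remains is that any exclusion would be unrecorded and made separately at six centres. Section 7.4 concedes that blinding the people who enter outcome data is unlikely to be practical. Such an exclusion could not be audited.

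A second reply is that the CRF and SAP are not at hand and may hold the item. The CRF might. But section 7.7 itself fixes what the definition needs on the database, and that statement is incomplete as written.

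A third reply is that the contamination shares are assumed. That is correct: at 2%, power is 0.849, essentially the stated 0.85. A reader might also infer that the observed rate cannot be compared with the 36% benchmark. The protocol does not say how that estimate handled cause, so non-comparability cannot be shown. The 50% limit also only raises a DSMC concern, and the committee could examine causes itself.

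Finally, a cause field completed by staff who may know the allocation could move events out of PGD differently by arm. That is a fair criticism of a bare yes/no field, and any remedy has to meet it.

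**Conclusion.** The point holds as a gap between the protocol's definition of PGD and the data it says the definition requires. As listed, the data set cannot show whether dysfunction with a known cause was excluded, and the PGD rate in its three uses may include such cases.

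The documents do not allow the size to be estimated. Under the assumption that 2% to 15% of hearts without PGD are counted in each arm, main-trial power at 200 per arm falls from 0.87 to between 0.85 and 0.68. The chance that a 25-patient arm with a true 36% rate passes the DSMC limit rises from 7% to between 10% and 33%. Both ranges illustrate consequence, not expected effect. The feasibility primary endpoint (3.3.1) does not use PGD and is unaffected. The change should be made because it is cheap and the information cannot reliably be reconstructed from the listed data afterwards.

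**What to change.** Add to the PGD list in 7.7 and to the 72-hour CRF: *discernible cause of graft dysfunction within 24 h: yes/no; if yes, which cause and on what evidence*. Allow the entry to be updated, with a date, when histology arrives after the 72-hour deadline. State in 7.7 that PGD requires the answer no.

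Because the person completing the field may know the allocation, also report by arm all graft dysfunction meeting the severity criteria regardless of cause, with known-cause cases listed separately. A difference between arms in how cases are attributed would then be visible.

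The cost is two or three CRF fields filled from existing records and a short addition to 7.7, with no new tests. The PGD rate may come out lower. Some subjectivity in the cause field remains, which the report regardless of cause exposes but does not remove.
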